4.1.7. Change from Baseline

Change from baseline for a given variable is defined as the value on a given Study Day (Time Point) minus the Baseline Value.

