5.9.3. Main Analytical Approach for First Key Secondary Endpoint

The change from baseline in log-transformed seizure frequency will be analyzed using an ANCOVA, including treatment as a factor and the log-transformed baseline focal onset seizure frequency per week as a covariate. The comparisons between the treatment groups will be based on the LS Mean difference between each CVL-865 dose group and placebo with corresponding 90% CI and P-value.

The LS Mean and 90%CI for each treatment group in log scale will be exponentiated to derive the model-estimated mean percent change from baseline using the following formula:

Estimated Mean % Change from Baseline=100*[1-exp(LSMean)]

The percent reduction relative to placebo and 90%CI will be constructed by exponentiating the LSMean difference and 90%CI between each CVL-865 treatment group and placebo from the ANOCOVA model using the following formula:

$$\% \frac{Reduction}{Placebo} = 100 * [1 - \exp(LSMean_{CVL-865} - LSMean_{Placebo})]$$

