5.11. Other Efficacy Analyses

5.11.1. Other Secondary Efficacy Endpoints

Other protocol-defined secondary efficacy endpoints will be summarized using descriptive statistics by treatment group and visit, if appropriate. Statistical analysis method for each endpoint is described below in Table 11. Statistical comparisons for each endpoint will be constructed without adjustment for multiple endpoints.

Table 11:	Summary of Other Secondary Efficacy Analyses

Endpoint	Analysis Population	Analysis Method
Seizure Freedom	mITT	Seizure freedom is defined as no seizures during the maintenance period. A logistic regression model with treatment as a fixed effect will be used. Odd ratios will be constructed for each CVL-865 treatment dose group compared with placebo and will be summarized with 90% confidence intervals. Should a logistic regression model fail to converge, paired Fisher's exact tests will be used instead.
Seizure Rate over Time	mITT	Seizure rate over time during the maintenance period will be analyzed using an MMRM. Only focal onset seizure will be included in this analysis. Data will be log-transformed using the convention ln(X+1), where X represents the seizure rate at each time point. Treatment group (CVL-865 7.5 mg, CVL-865 25 mg, or placebo), visit, and the interaction between treatment group and visit will be included as fixed factors in the MMRM, and log-transformed baseline rate will be included as a covariate. Subject will be included as a random effect, and an unstructured covariance structure will be used for the repeated measures. The difference between each CVL-865 level versus placebo at each visit will be estimated based on the LSMeans from the MMRM. The model estimated mean percent change from baseline and percent reduction versus placebo at each visit will be derived from back-transformed statistics the same way as described in Section 5.9.3 . A Mann-Whitney U test will also be used to compare each treatment level versus placebo at each visit.

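### SAP Table 11 borrows a percent-change formula that fits only change scores, and that formula in SAP 5.9.3 prints a fall in seizures as a positive change

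*SAP*

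**What the plan says.** Two parts of the SAP are linked by a cross-reference.

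- **Section 5.9.3, first key secondary endpoint.** The modelled variable is a change: "The change from baseline in log-transformed seizure frequency will be analyzed using an ANCOVA", with log baseline as covariate. Each arm's LSMean is then back-transformed as "Estimated Mean % Change from Baseline=100*[1-exp(LSMean" (the brackets close directly after). The contrast with placebo has the same algebraic form but is labelled a reduction: "The percent reduction relative to placebo and 90%CI will be constructed by exponentiating the LSMean difference and 90%CI".
- **Section 5.11.1, Table 11, Seizure Rate over Time.** The data description is "Data will be log-transformed using the convention ln(X+1), where X represents the seizure rate at each time point", and "log-transformed baseline rate will be included as a covariate". No subtraction of baseline is mentioned. The row then orders the within-arm percent change and the percent reduction versus placebo to be obtained by the 5.9.3 method: "The model estimated mean percent change from baseline and percent reduction versus placebo at each visit will be derived from back-transformed statistics the same way".

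Section 4.1.7 sets the sign convention for change from baseline: "the value on a given Study Day (Time Point) minus the Baseline Value". A fall is therefore negative. The primary endpoint follows the same direction (SAP 5.8.1: negative RRatio means fewer seizures).

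**The concern.** A back-transformation has to match the variable that was modelled. In 5.9.3, exp(LSMean) is a ratio to baseline, so one minus it is a proportionate fall. In Table 11 as literally described, exp(LSMean) is a rate plus one. Baseline enters only through covariate adjustment and is never subtracted, so the same formula no longer expresses change.

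The label in 5.9.3 is a separate matter. The expression is positive when seizures fall, yet it is called a percent change.

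At stake are the within-arm percent-change columns for the first key secondary endpoint (sign) and for a listed secondary endpoint (sign and, on the literal reading, the whole value). A reader of the report could take a +30% change as worsening. Independent programming (SAP 9.7) offers limited protection, because two programmers who follow the same written formula will agree with each other.

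**Working it through.** **Inputs.** Response and covariate: SAP Table 11. Back-transformation: SAP 5.9.3. Sign convention: SAP 4.1.7. Lowest eligible baseline: protocol inclusion criterion 4, 8 seizures in 8 weeks, so 8/8 = 1 per week. The plan gives no worked figure to reproduce. The rates below are illustrative.

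**Step 1: the formula where it belongs (5.9.3).** Let D be the LSMean of ln(T+1) - ln(B+1). Then exp(D) is the ratio of T+1 to B+1, and 100*[1-exp(D)] is the percent fall on the X+1 scale. For B = 4 and T = 2: D = ln(3/5), and 100*(1 - 0.60) = +40. The size is right for that scale, but a fall appears as a positive change.

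**Step 2: the formula applied to a level (Table 11, literal reading).** Let L be the LSMean of ln(X+1) and Xg = exp(L) - 1 the back-transformed rate. Then 100*[1-exp(L)] = 100*[1-(Xg+1)] = -100*Xg. Baseline does not appear.

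**Step 3: numbers (per week).**

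| Baseline B | Visit T | Table 11, literal | 5.9.3 as written, on change | 100*[exp(change)-1] | Raw change |
|---|---|---|---|---|---|
| 2 | 2 | -200% | 0% | 0% | 0% |
| 4 | 4 | -400% | 0% | 0% | 0% |
| 4 | 2 | -200% | +40% | -40% | -50% |
| 4 | 0 | 0% | +80% | -80% | -100% |
| 4 | 6 | -600% | -40% | +40% | +50% |
| 20 | 10 | -1000% | +47.6% | -47.6% | -50% |

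The gap between the last two columns comes from adding 1 before taking logs. That is a separate property of the transformation and is not part of this point.

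On the literal reading, any arm with a back-transformed rate above 1 per week prints a change below -100%, which cannot occur. Since eligible baselines start at 1 per week, such values would be common.

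**Step 4: what is not affected.** With log baseline as covariate, modelling the level or the change gives the same fit: subtracting ln(B+1) from every response lowers the baseline slope by 1 and leaves treatment differences unchanged. A simulated check used 1,000 subjects per arm, two visits, a random-intercept mixed model, median baseline near 4 per week with a floor of 1, and assumed rate multipliers of 1, 0.8 and 0.6 for placebo, low and high dose:

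| Model | LSMeans (placebo / low / high) | 100*[1-exp(LSMean)] | Reduction vs placebo (low / high) |
|---|---|---|---|
| Level | 1.672 / 1.487 / 1.302 | -432.3 / -342.6 / -267.5 | 16.86% / 30.96% |
| Change | 0.013 / -0.171 / -0.357 | -1.3 / +15.7 / +30.0 | 16.86% / 30.96% |

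The contrasts are identical. In the level row placebo shows the largest apparent fall, so the arms are ranked backwards. The two sets of LSMeans differ by one constant (1.672 - 0.013 = 1.659; 1.302 + 0.357 = 1.659), which is the overall mean of ln(B+1).

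**The case against.** The strongest reply is that Table 11 never names its dependent variable in so many words. It asks for a percent change by the 5.9.3 method, and 5.9.3 models a change. SAP 5.9.1.1 uses similar shorthand: its heading announces a change, while its text describes only ln(X+1) of the frequency. A programmer could reasonably model a change in Table 11, and then only the sign problem remains. This stands as a limit on certainty. The level reading is still the more literal one, because the CGI-S, QOLIE-31 and HUI rows of Table 11 say explicitly that they concern change from baseline, and the seizure-rate row does not.

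On the sign, it can be said that 100*[1-exp(LSMean)] is a correct percent reduction and only its label is wrong. That is true, and relabelling is an acceptable remedy. It can also be said that 4.1.7 defines an absolute change and that 5.9.4 gives no formula for its percent change, so a direct clash of signs with 5.9.4 is an inference. That is fair. The conflict with the value-minus-baseline convention remains.

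A reader might go further and infer that the seizure-rate-over-time endpoint is uninterpretable, or that the treatment comparison is compromised. The documents do not support this. The endpoint is the seizure rate itself. The SAP also provides LSMeans by visit, contrasts with placebo, descriptive summaries and a Mann-Whitney test, and the back-transformation of single-arm LSMeans touches none of these. Impossible values would probably be noticed at first output, which lowers the risk of a misleading report but does not correct the text.

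**Conclusion.** The point holds as a should-fix correction to reported secondary estimates, in two parts of different certainty.

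1. **Table 11.** On the literal reading, the within-arm percent change from baseline equals -100 times the back-transformed rate and carries no information about change: -200% at 2 per week from any baseline, 0% for a seizure-free arm. This assumes that the response is ln(X+1) at each visit, as the text describes. If a change score is intended, the text should say so.
2. **Section 5.9.3, and Table 11 through it.** On any reading the expression is a percent reduction under a percent-change label, so its sign runs against 4.1.7. The size is unaffected.

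The primary analysis, the hypotheses in SAP 5.3, the LSMeans, the percent reductions versus placebo and all p-values are untouched. The study is also declared exploratory (SAP 5.4). A must-fix grade is therefore not warranted.

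**What to change.** - **Table 11:** state that the MMRM response is the change from baseline in ln(X+1), keeping log baseline as covariate. If the level is kept as response, subtract the common overall mean of ln(B+1) at which the LSMeans are evaluated before back-transforming. Each arm's own baseline mean would be wrong here, because the LSMeans are adjusted to a common baseline.
- **Section 5.9.3 and Table 11:** report 100*[exp(LSMean change)-1], so that negative means a fall, with the 90% CI limits in matching order. Alternatively, keep the existing expression and relabel it as percent reduction from baseline; in that case the lower log-scale limit gives the upper percentage limit, and the reverse. Use one convention in both places.

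The cost is two lines of SAP wording and the corresponding code, with no effect on data collection, power or inference. It is best done before the SAP is final, since a later change would have to be documented as a deviation in the clinical study report (SAP Section 6).

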An additional key secondary endpoint is the 50% responder rate, defined as the percentage of subjects with at least a 50% reduction in the Maintenance Phase focal onset seizure frequency relative to the Baseline Period. This key secondary endpoint will be analyzed for the mITT population using a logistic regression model with effects for treatment. Odds ratios representing the odds of being a responder compared with placebo will be constructed for each CVL-865 treatment group. Subjects with missing or incomplete seizure information will be treated as non-responders for this analysis.

Continuous endpoints with repeated post-baseline assessments (CGI-S, CGI-I, PGIC) will be analyzed for the mITT population using a Mixed Model for Repeated Measures (MMRM). This estimand will include available post-baseline response data that occur before discontinuation of treatment. The baseline score (if applicable) will be included as the covariate, and treatment group (CVL-865 7.5 mg, CVL-865 25 mg, or placebo), visit, and the interaction between treatment group and visit will be included as fixed factors in the MMRM. The difference between each CVL-865 level versus placebo at each visit will be estimated based on the LSMeans from the MMRM. Changes from baseline in QOLIE-31 Domain and Overall Scores and HUI Utility Function scores will be analyzed using an analysis of covariance model (ANCOVA) with the baseline score and treatment group included in the model as fixed effects. The difference between each CVL-865 level versus placebo will be estimated based on the LSMeans from the ANCOVA model.

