3.1.3. Clinical Global Impression-Severity of Symptoms Scale

The CGI-S is an observer-rated scale that will be used to measure symptom severity. It is important to note that the observer or rater will provide their assessment of the subject's symptoms at the time of the current visit.

To perform this assessment, the investigator (or designee) will answer the following question: "Considering your total clinical experience with this particular population, how ill is the subject at this time?" Response choices are 0 = not assessed; 1 = normal, not at all ill; 2 = borderline ill; 3 = mildly ill; 4 = moderately ill; 5 = markedly ill; 6 = severely ill; and 7 = among the most extremely ill subjects.

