3.1.4. Clinical Global Impression-Improvement Scale

The CGI-I is an observer-rated scale that will be used to measure the subject's symptom severity compared with before initiation of treatment with IMP. It is important to note that the observer or rater will provide their assessment of the subject's current level of symptoms compared with their symptoms at baseline (Visit 1).

The investigator (or designee) will rate the subject's change from baseline in symptom severity (as related to seizure frequency and severity) using the following response choices: 0 = not assessed, 1 = very much improved, 2 = much improved, 3 = minimally improved, 4 = no change, 5 = minimally worse, 6 = much worse, and 7 = very much worse.

3.1.5. Quality of Life in Epilepsy – 31

The Quality of Life in Epilepsy – 31 (QOLIE-31) was developed in cooperation with professional postgraduate services, a division of Physicians World Communications Group and the QOLIE Development Group. The 31-item QOLIE-31 (Version 1.0) has been derived from the longer QOLIE-89 (Rausch & Crandall, 1982; Cramer et al, 1998).

The QOLIE-31 contains 7 multi-item scales that tap the following health concepts: emotional well-being, social functioning, energy/fatigue, cognitive functioning, seizure worry, medication effects, and overall quality of life. A QOLIE-31 overall score is obtained using a weighted average of the multi-item scale scores. The QOLIE-31 also includes a single item that assessed overall health.

Details of QOLIE-31 categories are provided in Section 9.2.

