PGI-C Score at Visits 2, 3, and 4	mITT	PGI-C score over time will be analyzed using a Mixed Model for Repeated Measures (MMRM) analysis. Treatment group (CVL-865 7.5 mg, CVL-865 25 mg, or placebo), visit, and the interaction between treatment group and visit will be included as fixed factors in the MMRM. Subject will be included as a random effect, and an unstructured covariance structure will be used for the repeated measures. The difference between each CVL-865 level versus placebo at each visit will be estimated based on the LSMeans from the MMRM.
CGI-S Score - Change from Baseline to Visits 2, 3, and 4	mITT	Change from baseline in CGI-S score over time will be analyzed using similar MMRM model as described above for PGI-C score.
CGI-I Score at Visit 2, 3, and 4	mITT	CGI-S score over time will be analyzed using similar MMRM model as described above for PGI-C score.
QOLIE-31 Overall and Domain Score - Change from Baseline to Visit 4	mITT	Changes from baseline in QOLIE-31 Overall Scores will be compared using an ANCOVA model with the baseline score as a covariate and treatment group included in the model as fixed effects in the mITT population. This estimand will include available post-baseline response data that occur before discontinuation of treatment or addition of rescue medication. The differences between each treatment dose group and placebo will be estimated based on the LSMeans difference between each CVL-865 dose group and placebo with corresponding 90% CI. The QOLIE-31 Domain Scores will be analyzed the same way, by each of the following categories: Energy, Emotions, Daily

Endpoint	Analysis Population	Analysis Method
		Activities, Mental Activity, Medication Effects, Seizure Worry, and Overall Quality of Life.
HUI Utility Score - Change from Baseline to Visit 4	mITT	Overall Health-Related Quality of Life (HRQL) Utility Scores (HUI-3 and HUI-2) will be analyzed using an ANCOVA model as described above for QOLIE-31 Overall Scores.

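### SAP Table 11 does not list the baseline covariate for CGI-S change that protocol 9.4.1 and SAP 5.5 call for; its CGI-I row names CGI-S, and no rule sets code 0 to missing

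*SAP*

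**What the plan says.** **CGI-S row, SAP Table 11.** The method is "Change from baseline in CGI-S score over time will be analyzed using similar MMRM model as described above for PGI-C score". The PGI-C row it points to starts with treatment group and goes on: "visit, and the interaction between treatment group and visit will be included as fixed factors in the MMRM. Subject will be included as a random" (cut here). No baseline score appears in either row.

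**CGI-I row, SAP Table 11.** The endpoint label is the CGI-I score at Visits 2, 3 and 4, but the method cell reads "CGI-S score over time will be analyzed using similar MMRM model as described above for PGI-C score".

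**Covariate rules elsewhere.** Protocol 9.4.1, on the repeated-measures model for CGI-S, CGI-I and PGIC together, says "The baseline score (if applicable) will be included as the covariate". SAP 5.5 sets a general rule that each efficacy variable's own baseline is a covariate in its analysis. SAP 4.1.6 defines the baseline for assessments outside the eDiary as the last value before first dose, and CGI-S is scheduled at Visit 1.

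**Response codes.** SAP 3.1.3 gives the CGI-S choices as "Response choices are 0 = not assessed; 1 = normal, not at all ill; 2 = borderline ill; 3 = mildly ill", continuing up to 7. SAP 3.1.4 gives those for CGI-I as "0 = not assessed, 1 = very much improved, 2 = much improved, 3 = minimally improved, 4 = no change", again up to 7. Protocol 8.2.3 and 8.2.4 list the same codes. On both scales 1 is the most favourable rating.

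**The concern.** Table 11 is the endpoint-specific specification, so it is the text most likely to be programmed. PGI-C is itself a rating of change and has no baseline, so its model is a poor template for a change score that does have one. A programmer following the CGI-S row would fit treatment, visit and interaction; one following SAP 5.5 would add baseline CGI-S. The two analyses give different estimates and standard errors, and nothing in Table 11 settles which is meant.

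The mislabelled CGI-I row leaves that endpoint, read literally, without a stated inferential model in the SAP, and describes an analysis of raw CGI-S scores that no endpoint calls for.

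The missing rule for code 0 matters because the scores go into a model as continuous values. If a stored 0 were carried through unrecoded, it would lie below the best rating. After baseline it would look like improvement; at baseline, for CGI-S, it would look like later worsening. The visit rules in SAP 4.3 prefer a scheduled record, so a scheduled 0 could also displace a real unscheduled rating.

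**Working it through.** The documents give no figure for the CGI analyses, so there is none to reproduce. The check sets the texts side by side and then sizes the two consequences under stated assumptions.

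**1. Is baseline written into comparable rows of Table 11?**

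| Row | Baseline term written in the row |
|---|---|
| Seizure rate over time | Yes, log-transformed baseline rate |
| QOLIE-31 (and HUI by reference) | Yes, baseline score |
| PGI-C | No; the scale has no baseline |
| CGI-S change | No; refers to the PGI-C model |
| Seizure freedom | No; treatment only |

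Two rows spell the covariate out. The seizure-freedom row, with treatment alone, shows that the general rule in SAP 5.5 is not reliably carried into the table. Silence in the CGI-S row can therefore be read either way.

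**2. What does the baseline term buy?** Assume equal variance s² at baseline and at the visit, with correlation r (not given in the documents).

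- Variance of unadjusted change: 2s²(1 − r)
- Residual variance after baseline adjustment: s²(1 − r²)
- Ratio, adjusted to unadjusted: (1 − r²) / [2(1 − r)] = (1 + r)/2

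| r | 1 − r² | 2(1 − r) | Ratio | Variance lower by |
|---|---|---|---|---|
| 0.3 | 0.91 | 1.40 | 0.65 | 35% |
| 0.4 | 0.84 | 1.20 | 0.70 | 30% |
| 0.5 | 0.75 | 1.00 | 0.75 | 25% |
| 0.6 | 0.64 | 0.80 | 0.80 | 20% |
| 0.8 | 0.36 | 0.40 | 0.90 | 10% |

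This is a single-visit approximation. The gain in the full repeated-measures model depends on how the baseline slope is specified across visits.

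**3. What would an unrecoded 0 do?** If k of n ratings with true mean m are stored as 0 and kept as numbers, the arm mean moves by −(k/n)m. With n = 40 evaluable per arm (SAP 1.2) and k = 1 (assumed):

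- m = 3: −3/40 = −0.075
- m = 4: −4/40 = −0.10
- m = 5: −5/40 = −0.125

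These are shifts in one arm's mean. Equal shares of zeros in arms with similar means would largely cancel in the treatment difference. With 0 set to missing, the direct shift is nil.

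**4. Is the intended CGI-I analysis recoverable?** Yes. The row label, SAP Table 2 and protocol 9.4.1 all identify CGI-I as the endpoint to be modelled.

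**The case against.** Read as a whole, the SAP already answers most of this. Section 5.5 is a general rule, the protocol agrees with it, and the CGI-S row says its model is similar to, not the same as, the PGI-C model. A careful analyst would add baseline CGI-S. The CGI-I slip is one letter, and its intent is plain. Code 0 is labelled as a non-rating, the programming conventions in SAP 9.7 count only non-missing observations in continuous summaries, and a visit that did not happen leaves no record rather than a stored 0. All these endpoints are other secondary endpoints in a study that SAP 5.4 calls exploratory.

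Much of that stands, and it rules out three stronger readings that a reader might infer:

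- *That the plan scores an unassessed visit as better than the best rating.* Neither document says so; they are silent on recoding. Nor does either suggest that remote or early-termination visits would produce zeros, or more of them in one arm.
- *That the SAP has decided on a CGI-S model without baseline.* SAP 5.5 and protocol 9.4.1 point the other way. This is an inconsistency, not a settled choice. An unadjusted change score would still use the baseline value, only less efficiently.
- *That CGI-I will go unanalysed.* SAP 5.11.1 commits to descriptive summaries of every other secondary endpoint, and protocol 9.4.1 names CGI-I for the repeated-measures model.

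What the objection does not remove is that the operative row and the general rule differ, that Table 11 does not follow SAP 5.5 in every row, and that no explicit rule covers code 0.

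**Conclusion.** The point holds as an inconsistency between the CGI-S row of Table 11 and both SAP 5.5 and protocol 9.4.1, together with a near-clerical error in the CGI-I row and an unstated missing-data rule for code 0. Its main substance is precision: a single-visit variance 20% to 30% lower with baseline CGI-S in the model than for unadjusted change, assuming correlations of 0.4 to 0.6 and equal variances (10% to 35% over correlations of 0.8 down to 0.3). Under randomisation, leaving baseline out would cost precision rather than bias the comparison. The code-0 shift of about 0.1 point per stray zero in 40 is purely illustrative. The primary and key secondary analyses are untouched. Severity: minor.

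**What to change.** Make three edits to the SAP:

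1. In the CGI-S row of Table 11, add *with baseline CGI-S score as a covariate*.
2. In the method cell of the CGI-I row, change *CGI-S* to *CGI-I*.
3. In SAP 3.1.3 and 3.1.4, or as a note to Table 11, state that a response of 0 is set to missing for both scales in all summaries and models, baseline included, before the visit-selection rules of SAP 4.3 are applied.

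Baseline CGI-S could also be a covariate for CGI-I. That is an optional gain in precision, not something the documents require: CGI-I has no baseline of its own, and the protocol limits the covariate to cases where it applies.

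The cost is a few lines of text and no new data, since CGI-S is already collected at Visit 1. The edits are best made before database lock, because SAP section 6 requires later departures from the final plan to be documented in the study report.

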15.	Subjects with other abnormal laboratory test results, vital sign results, or ECG findings unless, based on the investigator's judgment, the findings are not medically significant and would not impact the safety of the subjects or the interpretation of the trial results. The medical monitor should be contacted to discuss individual cases, as needed.									
	Tests with exclusionary results should be repeated to ensure reproducibility of the abnormality before excluding a subject based on criteria provided in this protocol. For ECGs, 3 consecutive recordings are required and if 2 of the 3 remain exclusionary, then the subject is not eligible for the trial.									
Disallow	ed Prior and Concomitant Medications									
16.	Subjects receiving more than 3 background AEDs for their epilepsy.									
17.	Subjects taking BZD medication chronically or who require a BZD (oral, intramuscular, or suppository) as rescue medication for epilepsy for more than 4 days on average over a 28-day period. (Note: a rescue BZD will be permitted if used ≤4 days on average over a 28-day period). During the Screening/Baseline Period, subjects requiring a BZD (oral, intramuscular, or suppository) as rescue medication for epilepsy more than 4 days on average over a 28-day period will be excluded.									

18.	Subjects taking other prohibited medications prior to randomization (as listed in Table 6) or who would be likely to require the use of prohibited concomitant medications during the trial (as listed in Table 7).
19.	Subjects taking any drug that is strong or moderate inducer/inhibitor CYP3A4 metabolism, which has the potential to alter CVL-865 exposure levels (see Section 6.5).
20.	Subjects taking any drug that is a sensitive P-gp and BCRP substrate (see Section 6.5).
21.	Vigabatrin is excluded as a concomitant AED, unless subject has been taking it for at least 2 years prior to signing the ICF and have no evidence of visual field defects on at least 2 visual field tests within 6 months of signing the ICF.
22.	Felbamate is excluded as a concomitant AED, unless subject has been taking it for at least 2 years prior to signing the ICF, with a stable dose for $\geq$ 49 days, and have acceptable hematology and liver function test values (or discontinued felbamate no less than 49 days prior to signing the ICF).
Other	
23.	Female subjects who are breastfeeding and/or who have a positive pregnancy test result prior to receiving IMP.

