5.8.2. Primary Estimand

The key research question for the primary endpoint will be addressed with an estimand based on the following attributes:

- 1. Treatments: treatments as randomized regardless of the actual treatment received.
- 2. Target study population of interest: subjects in the modified intent-to-treat (mITT) population.
- 3. Endpoint (variable) of interest: RRatio over the Maintenance Phase.
- 4. Population level summary of interest: difference between CVL-865 treated and placebo subjects in RRatio over the Maintenance Phase.
- 5. Strategy for Intercurrent events (ICEs): a hypothetical strategy will be used to address intercurrent events (ICEs) of potential death, and treatment discontinuations. The data after treatment discontinuations will typically be missing or be treated as missing even if collected. Under the hypothetical strategy, these missing values as the result of ICEs of discontinuation will be assumed to follow the observed trajectory of the subject and thus the endpoint will include only eDiary based response data that occur before discontinuation of treatment. It should be noted that the use of protocol defined rescue medication will not be considered as an ICE.

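### SAP Table 11 cuts QOLIE-31, and apparently HUI, at an undefined addition of rescue medication; this can remove a rescued subject's only scheduled post-baseline value, although rescue is not an intercurrent event for the main endpoints

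*SAP*

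**What the plan says.** The QOLIE-31 row of SAP Table 11 (section 5.11.1) is labelled "QOLIE-31 Overall and Domain Score - Change from Baseline to Visit 4" and specifies an ANCOVA in the mITT population. Its data rule is: "This estimand will include available post-baseline response data that occur before discontinuation of treatment or addition of rescue medication". The SAP does not define when rescue has been added.

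The HUI row, "HUI Utility Score - Change from Baseline to Visit 4", has no data rule of its own. It says that the utility scores "will be analyzed using an ANCOVA model as described above for QOLIE-31 Overall Scores".

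The three fully specified estimands treat rescue differently. SAP 5.8.2 (primary) says that "the use of protocol defined rescue medication will not be considered as an ICE", and 5.9.2 and 5.10.1 repeat this for the two key secondary endpoints.

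Rescue is part of the design. Under Protocol 5.2, criterion 17, "a rescue BZD will be permitted if used" on no more than 4 days per 28 on average; this is an entry and baseline limit. Protocol 6.5.2 allows benzodiazepines during the trial apart from listed exceptions, and Protocol 6.5.3 gives habitual users an approved individual rescue plan.

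Protocol 9.4.1 says "Changes from baseline in QOLIE-31 Domain and Overall Scores and HUI Utility Function scores will be analyzed" by ANCOVA, with no rescue condition. For CGI-S, CGI-I and PGIC it cuts the data at treatment discontinuation only.

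**The concern.** Rescue use happens after randomisation and is related to seizure control, which the drug is meant to change. If values are dropped because of rescue, the two arms are compared among subjects who did not need it, and randomisation does not protect that comparison. A rescued subject's seizure counts would remain in the primary analysis while the same subject's Visit 4 quality-of-life scores were set aside, so the two sets of results would describe different subjects without a stated reason.

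The undefined trigger adds a second problem. Two programmers could build different analysis sets from the same sentence. Reporting of rescue use is only an optional exploratory output (SAP 5.12), so a reader might not see how many subjects were excluded, or from which arm.

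**Working it through.** **1. How many values a subject has.** The schedule of assessments places QOLIE-31 and HUI at Visit 1, Visit 4 and early termination only. SAP Table 8 assigns every early-termination or unscheduled value from Day 2 onward to Visit 4. Each subject therefore supplies one post-baseline analysis value. Visit 4 comes after 2 + 8 = 10 weeks of treatment, so rescue has 10 weeks in which to occur first.

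**2. What happens after rescue.** If the trigger is any rescue use, a Visit 4 value that follows rescue is not usable. A value obtained before rescue at an unscheduled or early-termination visit would still count through Table 8. Otherwise the subject leaves the ANCOVA: there are no repeated measures, and the sensitivity analyses in 5.8.4, 5.9.4 and 5.10.3 cover only the primary and key secondary endpoints. If the trigger is only newly started rescue, fewer subjects are lost.

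**3. The plan's own sizing figure.** The only one is for RRatio: difference 20, SD 34, two-sided alpha 0.1, 50 randomised and 40 evaluable per arm (SAP 1.2).
- n = 2 × (1.645 + 0.842)² × (34/20)² = 35.7, so 36 per arm; 36/0.8 = 45, below the planned 50.
- Power with 40 per arm is 83.8% (normal approximation) or 83.2% (t-test), consistent with the stated minimum of 80%.

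This figure reproduces. It concerns RRatio, and 40 per arm is borrowed below only as a base.

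**4. Precision.** No rescue rate is given, so the share r rescued before Visit 4, equal in both arms, is an assumption. With an unchanged SD, the standard error is multiplied by 1/√(1 − r). The power column uses the primary's standardised effect, 20/34 = 0.59 SD, purely as an illustration.

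| Assumed r | n per arm | SE rises by | Illustrative power |
|---|---|---|---|
| 0% | 40 | 0% | 83.8% |
| 10% | 36 | 5% | 80.3% |
| 20% | 32 | 12% | 76.1% |
| 30% | 28 | 20% | 71.1% |
| 40% | 24 | 29% | 65.3% |

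**5. Selection.** Let d be the active-minus-placebo difference among never-rescued subjects, with higher scores better. Let p0 and p1 be the rescue rates on placebo and active, and let rescued subjects score g SD lower in both arms. The difference with everyone kept is d + g(p0 − p1). Dropping rescued subjects leaves d, a shift of −g(p0 − p1). For assumed g from 0.3 to 0.8:
- 20% v 10%: −0.03 to −0.08 SD
- 30% v 15%: −0.045 to −0.12 SD
- 40% v 20%: −0.06 to −0.16 SD
- equal rates: zero

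Reversing the rates reverses the sign: 15% on placebo and 30% on active gives +0.045 to +0.12 SD. If the deficits also differ (g0 on placebo, g1 on active), the shift is g1·p1 − g0·p0, which need not be zero even when rates are equal.

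**The case against.** Estimands are specific to an endpoint, so a rule that differs from the seizure endpoints is not in itself an error. There is a plausible motive: Protocol 2.2 notes sedation and psychomotor impairment with benzodiazepines, and QOLIE-31 scores energy, mental activity and medication effects. A quality-of-life estimand free of rescue could be defended. Protocol 9.4.1 sets no cut-off at all for QOLIE-31 or HUI, and Protocol 9.4 leaves full detail to the SAP, so the SAP contradicts no protocol rule. All of this stands. However, removing rescued subjects from a complete-case ANCOVA does not validly estimate what would have happened without rescue, and the SAP states neither that target nor a reason.

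A reader might go further than the documents allow in three ways.
- One might infer that a single rescue dose at any time certainly excludes a subject. Continued use under an approved rescue plan need not be an addition, and an earlier early-termination or unscheduled value would still count.
- One might infer that the bias runs against the drug. Neither document gives rescue rates by arm, and habitual rescue is partly a trait present before randomisation, which should balance on average.
- One might take the HUI exclusion as settled. The HUI row imports the ANCOVA; that it also imports the data cut-off is the natural reading but remains an inference.

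**Conclusion.** The point holds as an unexplained inconsistency built on an undefined term, with a real risk of selection bias and lost precision for QOLIE-31 and apparently HUI. Under the any-use reading, the standard error rises by about 5% to 29% for assumed rescue rates of 10% to 40%. The illustrative selection shifts, up to 0.16 SD, rest entirely on assumed rates and deficits. The shift is zero if both are equal across arms, and it is against the drug only if, for example, the drug reduces rescue. The actual direction and size cannot be derived from the documents. Both are other secondary endpoints in a trial that SAP 5.4 calls exploratory; primary and key secondary inference is untouched.

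**What to change.** Delete the last five words of the quoted sentence in the QOLIE-31 row of Table 11, so that QOLIE-31 and HUI keep on-treatment Visit 4 data regardless of protocol-defined rescue, in line with SAP 5.8.2. The HUI row should say so explicitly.

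If a rescue-free analysis is wanted, keep it as supplementary, define what counts as adding rescue, and state whether it applies to HUI.

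The cost is a short SAP edit before database lock, with no change to conduct or data collection. The small downside is that the estimate then includes any direct effect of rescue benzodiazepine on quality of life.
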